6. TRIAL OBJECTIVES AND PURPOSE

This study will be an open-label, non-interventional 12-week extension of the Parent study.

6.1. Primary Objective

To assess the safety and tolerability of a single dose of CLS-AX in subjects with neovascular age-related macular degeneration up to 24 weeks following administration of CLS-AX at Visit 2 (Baseline, Day 1) in the Parent study.

6.2. Secondary Objectives

To evaluate the effect of a single dose of CLS-AX on visual function and ocular anatomy and the need for additional treatment for symptoms of nAMD up to 24 weeks following administration of CLS-AX at Visit 2 (Baseline, Day 1) in the Parent study.

7. INVESTIGATIONAL PLAN

7.1. Overall Study Design

This is an open-label, non-interventional extension study of up to 12 weeks in duration in subjects participating in and completing Cohorts 2, 3 and 4 of the Parent study, CLS1002-101.

[REDACTED]

The Parent study design includes 4 dose cohorts of approximately 5 enrolled subjects in each cohort. Subject eligibility will be established at Visit 1, Screening (Day -28 ± 3 days). Eligible subjects will receive an IVT injection of aflibercept, 2 mg (0.05 mL), at Visit 1 (Screening), followed by a suprachoroidal injection of CLS-AX at Visit 2, Baseline (Day 1) upon enrollment.

[REDACTED]

This extension study includes 4 clinic visits (Enrollment Day, and Visits 6, 7 and 8; Weeks 12, 16, 20 and 24) over a maximum of 12 weeks, for a total of up to 24 weeks follow-up from the time of CLS-AX administration at Visit 2 (Baseline, Day 1) in the Parent study.

[REDACTED]

[REDACTED]

To ensure subjects have adequate time to evaluate and provide informed consent to participate in the extension study, consent may be obtained prior to, as part of, or after Visit 5 (no later than within 48 hours) of the Parent study. Eligibility assessments will only be performed after consent has been obtained and after all the Visit 5 assessments of the Parent study have been completed and the subject has exited the Parent study.

[REDACTED]

[REDACTED]

Post additional treatment assessment of the study eye will be conducted.

Ideally, Enrollment Day assessments should occur on the same day as Visit 5 of the Parent study especially for those subjects who met additional therapy criteria at Visit 5 of the Parent study and were administered additional therapy, so that post therapy assessments may be performed as part of this extension study's Enrollment Day. If due to time constraints, it is not possible to conduct post therapy assessments on the same day as the injection of the additional therapy after exiting Visit 5 of the Parent study, the assessments should occur no later than within 48 hours of having received the additional therapy, upon exiting the Parent study at Visit 5.

The 3 dose cohorts from the Parent study that will be enrolled into this extension study include the following doses:

- [REDACTED]
- [REDACTED]
- [REDACTED]

Subjects enrolled into this extension study will participate in three monthly follow-up visits (Visits 6, 7 and 8; Weeks 16, 20 and 24) [REDACTED]

[REDACTED] The determination whether additional treatment is needed will include reference to data collected during the Parent study (Section 9.4.1).

Criteria for the early termination or suspension of the study are described in Section 7.5.

See Section 20 for the Time and Events Schedule.

7.2. Endpoints

In this extension study, Baseline will be defined as the last non-missing value prior to CLS-AX administration at Visit 2 (Day 1) in the Parent study, CLS1002-101.

7.2.1. Primary Endpoint

The primary endpoint for evaluating the continued tolerability of the three dose cohorts will be based on the number of subjects experiencing treatment-emergent (TEAEs), and serious adverse events (SAEs). Treatment-emergent adverse events are defined as an event that emerges following treatment with CLS-AX (administered at Visit 2 (Baseline, Day 1) of the Parent study, CLS1002-101), having been absent pre-treatment or worsens relative to the pre-treatment state.

7.2.2. Secondary Endpoints

Secondary endpoints for evaluating the tolerability and the effect of the three dose cohorts will include:

- [REDACTED]
- [REDACTED]
- [REDACTED]
- [REDACTED]
- [REDACTED]

7.3. Number of Subjects

The study population will include a maximum of 19 subjects (up to approximately 5 subjects each from Cohorts 2, 3 and 4) that successfully complete and exit the Parent study without receiving prohibited medication. Medications prohibited in the Parent study will continue to be prohibited in this extension study and are defined in Section 9.5.1.

The expected duration of participation in the extension study is up to 12 weeks from study entry. The complete inclusion and exclusion criteria are presented in Section 8.

7.4. Treatment Assignment

This is an open-label, non-interventional extension study of the Parent study, CLS1002-101. There will be no investigational product dispensed or administered in this study.

7.5. Criteria for Study Termination

7.5.1. Early Discontinuation of the Study

The study or parts of the study may be discontinued by the Sponsor, at any time. If the clinical study is prematurely terminated, the Sponsor will inform the Investigators and the regulatory authorities of the termination and the reason(s) for the termination, and subjects will be asked to complete study assessments at Visit 8 (Study Exit, Week 24). The Investigator should promptly notify the Institutional Review Board (IRB) or Independent Ethics Committee (IEC) of the termination and of the reasons.

7.5.2. Suspension of the Study

The study enrollment will be immediately suspended, and no additional subjects will be enrolled upon suspension of the Parent study.

If the clinical study is suspended, the Sponsor will inform the Investigators and the regulatory authorities of the suspension and the reason(s) for the suspension. The Investigator should promptly notify the IRB or IEC of the suspension and of the reasons.

Enrollment of subjects into the study will not be restarted until the Sponsor and the Safety Monitoring Committee have agreed to the course of action to be taken in the Parent study and the IRB/IEC has been notified.

During the period of suspension of enrollment, provided the Investigator determines that it is in the subjects' best interest to continue in the study, subjects currently enrolled in the extension study will continue with the protocol specified visit schedule. The Sponsor's preference is to retain enrolled subjects in the extension study until the final study visit (Visit 8, Week 24).

8. SELECTION AND WITHDRAWAL OF SUBJECTS

Subject eligibility will be determined on Enrollment Day which may be the same day as the final visit (Visit 5) of the Parent study after the subject has exited the Parent study or within no later than 48 hours of exiting the Parent Study.

8.1. Subject Inclusion Criteria

Subjects are eligible for participation in this study if s/he meets all of the following criteria:

1. Enrolled in and completed the Parent study, CLS1002-101, as part of Cohort 2, Cohort 3, or Cohort 4.
2. Understands the language of the informed consent; willing and able to provide written informed consent prior to any study procedures; willing to comply with the instructions and attend all scheduled study visits.
3. Subjects of childbearing potential must agree to use acceptable methods of contraception throughout participation in the study. Acceptable methods of contraception include double barrier methods (condom with spermicide or diaphragm with spermicide), hormonal methods (oral contraceptives, implantable, transdermal, or injectable contraceptives), or an intrauterine contraceptive device with a documented failure rate of less than 1% per year. Abstinence may be considered an acceptable method of contraception at the discretion of the Investigator, but the subject must agree to use one of the acceptable birth control methods if he or she becomes sexually active. Females of childbearing potential must consent to performance of a pregnancy test,

8.2. Subject Exclusion Criteria

Subjects are ineligible for participation in this study if s/he meets any of the following criteria:

1. [REDACTED]
2. Enrolled in the Parent study CLS1002-101 as part of Cohort 1.
3. Females of childbearing potential who are pregnant and or lactating.

8.3. Subject Withdrawal Criteria

Subjects may withdraw from the study at any time and for any reason without obligation. Subjects may be removed from the study at the Investigator's discretion or if they require additional therapy due to disease progression that warrants further treatment. Investigators may withdraw a subject from the study because a new health condition appears or an existing condition worsens that requires care or medication prohibited by the protocol and it is in the subject's best interest to exit the study, according to the Investigator's clinical judgement. In the event that a subject develops a medical condition that requires treatment with a medication prohibited by this protocol (i.e., if the treating physician determines, using best medical

judgment, that such medications are medically necessary for the subject's welfare), then a protocol deviation will be recorded. In such cases, provided the Investigator determines that it is in the subject's best interest to continue in the study, the Sponsor's preference is to retain such subjects in the study. For a list of prohibited medications, please see Section 9.5.1.

Subjects who withdraw prematurely from the study will be asked to complete Visit 8 (Study Exit) study assessments. For subjects who withdraw consent, no further related activities will be conducted. If an SAE is unresolved at the time of the subject's final study visit, the Investigator should make every attempt to follow up until the SAE is resolved or stabilized, the subject is lost to follow-up, or there is some other resolution of the event.

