8.4. Visit Procedure Description

8.4.1. General Procedures

The study will consist of 4 study visits over approximately 12 weeks. Subjects are expected to attend all study visits.

Written informed consent will be obtained for each subject before any study-specific assessments are performed. To ensure subjects have adequate time to evaluate and provide informed consent to participate in the extension study, consent may be obtained prior to, as part of, or after Visit 5 (no later than within 48 hours) of the Parent study. Subject eligibility will be established on the Enrollment Day which may be on the same day as the final visit (Visit 5) of the Parent study after the subject has exited the Parent study or no later than within 48 hours of exiting the Parent Study. If a subject was assessed to have met additional treatment criteria at Visit 5 of the Parent study, data of the additional treatment given will be collected at Enrollment Day.

Ideally, Enrollment Day assessments should occur on the same day as Visit 5 of the Parent study especially for those subjects who met additional therapy criteria at Visit 5 of the Parent study and were administered additional therapy, so that post therapy assessments may be performed as part of this extension study's Enrollment Day. If due to time constraints, it is not possible to conduct post therapy assessments on the same day as the injection of the additional therapy after exiting Visit 5 of the Parent study, the assessments should occur no later than within 48 hours of exiting the Parent study at Visit 5.

Additional safety follow-up visits will occur approximately every 4 weeks through Week 24 (Visits 6, 7 and 8; Weeks 16, 20 and 24, respectively). At Visits 6, 7 and 8 subjects will be evaluated to determine any need for additional treatment based on pre-defined criteria (Section 9.4.1).

If the subject's study eye qualifies for additional therapy at the final visit (Visit 5) of the Parent study or Visits 6 or 7 (Weeks 16 or 20) and receives additional therapy as a result, then ocular safety will be assessed in the study eye only following administration of the additional therapy.

The final visit of the extension study occurs at Visit 8 (Week 24). If the subject's study eye qualifies for additional therapy at the final visit (Visit 8) of the extension study and receives additional therapy as a result, data of the treatment administered will be collected whenever possible.

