8.4.2.2. Enrollment Day - Post Administration of Additional Therapy

The following assessments must be performed on the study eye after administration of additional therapy if the subject's study eye qualifies for additional therapy at the final visit (Visit 5) of the Parent study and receives additional therapy as a result.

1. Assess adverse events (AEs).

2. Review changes to concomitant medications.
3. Perform ophthalmic assessments on the study eye only:

4. Schedule time for subject to return for the next visit.

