8.4.4. Visit 8 (Week 24) End of Study/Early Termination

Visit 8 (Week 24) is the final study visit. Subjects who prematurely discontinue from the study should also complete all Visit 8 assessments.

1. Confirm study eye (Section 9.2).
2. Assess AEs.
3. Review changes to concomitant medications.
4. Obtain vital signs by performing [REDACTED]
[REDACTED]
5. Assess for changes to medical and ocular history.
6. Perform a review of body systems.
7. Collect urine and perform pregnancy test in females of childbearing potential.
8. Perform ophthalmic assessments on both eyes:

9. Perform photographic evaluations on both eyes:

10. Determine if the subject's study eye qualifies for the additional therapy according to the Additional Therapy Criteria listed in Section 9.4.1. Subjects satisfying the additional therapy criteria at Visit 8 (Week 24) will complete all Visit 8 assessments per protocol, exit the study and revert to standard of care as determined by the Investigator. Data of the additional therapy administered will be collected whenever possible. Subjects will then be released to the physician's care.

NOTE:

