9.4.1. Additional Therapy Criteria

At Visit 6 (Week 16), Visit 7 (Week 20) and Visit 8 (Week 24) of this extension study, subjects will be evaluated for the need for additional therapy for nAMD in the study eye based on the following criteria:

- 
- 
- 

If the pre-defined criteria are met at Visits 6 and/or 7 (Weeks 16 and/or 20), then additional therapy consisting of an IVT injection of aflibercept 2 mg (0.05 mL), ranibizumab 0.5 mg (0.05 mL), bevacizumab 1.25 mg (0.05 mL), or brolucizumab 6 mg (0.05 mL), as determined by the Investigator, may be administered; even if additional therapy is given, the subjects will remain in the study and will be followed until Visit 8 (Study Exit). Subjects satisfying the additional therapy criteria at Visit 8 (Study Exit) will complete all Visit 8 assessments per protocol, exit the study and revert to standard of care as determined by the Investigator. Data of the additional therapy administered will be collected whenever possible.

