9.5.1. Prohibited Medications

Subjects must not receive any treatments in the study eye for nAMD or any systemic treatments for nAMD not approved in the protocol. The list of prohibited treatments provided below is not intended to be comprehensive, but rather to help guide the Investigator's medical judgment. In cases where a subject presents with a treatment not included on the following list or should there be any question on the part of the Investigator, Investigators are encouraged to confer with the Medical Monitor for any clarification.

Use of the following treatments is prohibited at any time during the study:

In cases where there is anticipated need for any of the treatments listed here during the study (post Visit 5), or if a subject presents to the Investigator having initiated treatment during the study with one of these treatments, it is the responsibility of the Investigator to notify the Sponsor immediately. If additional therapy is necessary to treat worsening of nAMD in the study

eye and normal standard of care requires additional intervention, the treatment(s) should be recorded in the subject's source document(s) and CRF and should follow the guidelines presented for additional therapy criteria. Subjects will not be discontinued from the study because of initiation of or change in a prohibited medication. Any use of a prohibited medication will be documented as a protocol deviation.

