11.2.3. Recording Adverse Events

Adverse events spontaneously reported by the subject and/or in response to an open question from the study personnel or revealed by observation will be recorded during the study at the investigational site on the CRF. Information about AEs will be collected from the time of signing of the consent form until 30 days after the end of study participation. Detailed information regarding all SAEs should be collected from the signing of the informed consent until the end of the study. SAEs that are considered related to the use of study drug, SCS

Microinjector, and/or study procedure by the Investigator may be reported by the Investigator if they occur after the end of the study. The Investigator must continue to follow the patient until the SAE has resolved, the condition has become chronic in nature, the condition stabilizes (in the case of persistent impairment), the patient experiences a fatal outcome or is lost to follow up.

The AE term should be reported in standard medical terminology as concisely as possible. In general, the AE recorded should not be a procedure, outcome, or clinical/laboratory measurement, but should reflect the event leading to the procedure, outcome, or the cause of the clinical/laboratory abnormality, if known. Whenever possible, AEs should be evaluated and recorded as a diagnosis, rather than as individual signs or symptoms. However, if a definitive diagnosis is not possible, the individual signs and symptoms should be recorded. For each AE, the Investigator will evaluate and report the onset (date and time), resolution (date and time), intensity, causality, action taken, seriousness, outcome (if applicable), and whether or not it caused the patient to discontinue the study.

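### Section 8.3 allows removal of a subject for needing additional therapy, while Section 9.4.1 keeps treated subjects in the study to Visit 8

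*Combined protocol and SAP*

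**What the plan says.** Section 8.3 (Subject Withdrawal Criteria) gives two grounds for removal in one sentence: "Subjects may be removed from the study at the Investigator's discretion or if they require additional therapy due to disease progression that warrants further treatment".

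Section 9.4.1 (Additional Therapy Criteria) covers subjects who meet the criteria at Visit 6 or 7 and may then receive one of the listed anti-VEGF injections. It says that "even if additional therapy is given, the subjects will remain in the study and will be followed until Visit 8 (Study Exit".

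Other sections bear on the same point:

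- Section 8.4.1: "Subjects are expected to attend all study visits".
- Sections 8.4.2.2 and 8.4.3.2, on procedures after additional therapy, require study-eye assessments and both end with the same step: "Schedule time for subject to return for the next visit".
- Section 9.5.1: treatment for worsening nAMD in the study eye "should follow the guidelines presented for additional therapy criteria". The same section says that starting or changing a prohibited medication does not lead to discontinuation.
- Section 6.2 includes in the secondary objective "the need for additional treatment for symptoms of nAMD up to 24 weeks following administration of CLS-AX", alongside visual function and ocular anatomy.

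Two provisions soften an early exit. Section 8.4.4: "Subjects who prematurely discontinue from the study should also complete all Visit 8 assessments". Section 11.2.3: "Information about AEs will be collected from the time of signing of the consent form until 30 days after the end of study participation".

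**The concern.** A subject who needs additional therapy at Week 16 or 20 falls under two rules with different results. Section 8.3 permits removal and Section 9.4.1 requires follow-up to Visit 8. The visible text does not say which prevails.

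Need for additional therapy is one of the outcomes this extension was set up to describe, and Section 5 gives durability of effect as its rationale. Removal on that ground would be dropout caused by the outcome. The subjects lost would be those whose disease had become active again. Their later acuity, retinal thickness, repeat-therapy and scheduled ocular safety data would be lost with them. Sites that relied on different sections could also handle similar subjects differently, so follow-up could vary between cohorts for reasons unrelated to dose.

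**Working it through.** The plan gives no figure to reproduce. Section 12.2 states that the sample size is not statistically driven and that no formal testing is planned. The check is therefore a comparison of texts, followed by simple arithmetic on what one removal costs.

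**1. Do the sections conflict?**

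| Section | Situation | Consequence for the subject |
|---|---|---|
| 8.3 | Needs additional therapy for disease progression | May be removed |
| 9.4.1 | Given additional therapy at Visit 6 or 7 | Stays to Visit 8 |
| 8.4.3.2 | Given additional therapy at Visit 6 or 7 | Assessed, then booked for the next visit |
| 8.4.2.2 | Given additional therapy after qualifying at parent Visit 5 | Assessed on Enrollment Day, then booked for the next visit |
| 9.5.1 | Starts a prohibited medication | Not discontinued for that reason |

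In Section 8.3 the need for therapy is joined to investigator discretion by *or*, so it is a separate ground. The clause uses the protocol's own term for rescue treatment and does not limit it to therapy outside Section 9.4.1. The sponsor's preference for retention, later in Section 8.3, is attached to prohibited-medication cases and not to this clause. Read literally, permitted rescue is a ground for removal while a prohibited drug is not.

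Exit at Visit 8 after meeting the criteria is handled the same way in every section and is not part of the conflict.

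**2. Share of a cohort lost per removal.** Section 12.2 gives about 5 subjects in each of three cohorts and a maximum of 19.

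- Cohort of 5: 1/5 = 20%.
- Cap spread evenly: 19/3 = 6.3 per cohort, and 1/6.3 = about 16%.

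Section 12.5.8 specifies no imputation.

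**3. Scheduled visits lost.** After Enrollment Day the follow-up visits are at Weeks 16, 20 and 24.

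- Removal at Week 16 loses Weeks 20 and 24, which is 2 of 3.
- Removal at Week 20 loses Week 24, which is 1 of 3.

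Exit assessments are requested in both cases, but they describe the eye at Week 16 or 20 and not at Week 24.

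**4. Adverse event time before Week 24 without routine collection.** Days from removal to Week 24, minus the 30 days of collection after participation ends:

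- Week 16: (24 − 16) × 7 = 56 days; 56 − 30 = 26 uncovered.
- Week 20: (24 − 20) × 7 = 28 days, which is less than 30, so 0 uncovered.

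**5. How many subjects could the clause reach?** The documents give no rate for Cohorts 2 to 4. In parent Cohort 1, 2 of 6 completed without meeting the criteria (Section 5), so up to 4 of 6 (67%) met them or did not complete. The rates below are assumed, for illustration only:

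| Assumed rate | Of 5 | Of 15 (3 × 5) | Of 19 |
|---|---|---|---|
| 20% | 1 | 3 | 3.8 |
| 40% | 2 | 6 | 7.6 |
| 67% | 3.3 | 10 | 12.7 |

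These are subjects whom the clause could touch, not a forecast of removals. Cohort 1 had a different dose and a 12-week window, and the clause is permissive.

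**The case against.** The best defence is that the two sections can be read together. Section 8.3 is general and permissive, while Section 9.4.1 is specific and directive, so an investigator working from the additional-therapy section is told to keep the subject. Section 9.4.1 also speaks only of therapy at Visits 6 and 7. It says nothing about emergency treatment under Section 9.4 or therapy at an unscheduled visit, and Section 8.4.5 foresees that an unscheduled visit may end in discontinuation. Section 8.3 could be meant for those cases. That reading fails because Section 8.3 does not confine itself to them and Section 8.4.5 only says how to document such a visit. General discretion and the best-interest exit already cover the cases on which Section 9.4.1 is silent.

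Several points do stand:

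- Only Section 9.4.1 states retention to Visit 8 outright. The attendance expectation and the scheduling steps support it but would not settle the matter alone.
- Losing 1 in 5 is the cost of any dropout in a cohort of that size, whatever the cause.
- The event that triggers removal is recorded before the subject leaves. Adverse events already reported are followed to resolution or stability (Section 11.2.5), and related SAEs remain reportable after the study (Section 11.2.4).
- Readings taken after an anti-VEGF injection do not isolate the effect of a single dose of CLS-AX.
- Investigator discretion remains after the deletion, so deletion alone would not prevent removals. The added sentence is needed.
- Some nearby text is redacted, so the absence of a precedence rule can be confirmed only for the visible text.

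**Conclusion.** The concern holds. Section 8.3 contradicts Section 9.4.1 in the current protocol text, and the other visible provisions on treated subjects favour retention.

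The consequence is bounded. It arises only if an investigator uses the clause. Each use then removes about 16% to 20% of a cohort from later summaries, costs 1 or 2 of the 3 follow-up visits, and leaves 0 to 26 days before Week 24 without routine adverse event collection. These figures assume cohorts of 5 to 6.3 subjects and removal at the scheduled Week 16 or 20 visit. The number of removals is unknown. The size and sign of any shift in mean acuity cannot be derived either, because retained eyes may recover after rescue. The study is descriptive, so no power or error rate is affected.

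The wording should be corrected because the conflict is plain and the repair is almost free.

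**What to change.** In Section 8.3, delete the second half of the removal sentence, from the word *or* onward, so that investigator discretion is the only ground left in it. Then add a sentence such as: *Receipt of additional therapy is not by itself a reason for removal; these subjects continue to Visit 8 as described in Section 9.4.1.* Leave the best-interest exit for new or worsening health conditions unchanged.

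The cost is one phrase deleted and one sentence added at the next amendment, with no extra visits, procedures or subjects.
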